10.1.4 Adverse events of special interest (specific adverse events)

An AE of Special Interest (AESI) (serious or non-serious) is one of scientific and medical concern specific to the study drug, for which ongoing monitoring and rapid communication by the principal investigator or investigator to Takeda may be appropriate. Such events may require further investigation in order to establish assessment, and instructions provided to investigators on how and when they should be reported to the sponsor are described in Section 10.2.1.3.

AESIs: Hypoglycemia-related AEs, intestinal obstruction-related AEs and acute pancreatitis-related AEs (for both Trelagliptin and Alogliptin), QT/QTc interval prolongation-related AEs (for Trelagliptin), and Liver dysfunction or jaundice-related AEs (for Alogliptin).

<For both Trelagliptin and Alogliptin>

[Hypoglycemia-related AEs]

Hypoglycemia-related AEs are designated as AESIs because, in general, attention should be paid to the events in the treatment of diabetes mellitus.

[Intestinal obstruction-related AEs]

Intestinal obstruction-related AEs are designated as AESIs because there are accumulated reports of intestinal obstruction as an adverse reaction to similar incretin-related drugs (GLP-1 receptor agonists and other DPP-4 inhibitors).

[Acute pancreatitis-related AEs]

Acute pancreatitis-related AEs are designated as AESIs because there are accumulated reports of acute pancreatitis as an adverse reaction to similar incretin-related drugs.

<For Trelagliptin>

[QT/QTc interval prolongation-related AEs]

QT/QTc interval prolongation-related AEs are designated as AESIs because, in the QT/QTc assessment study conducted during the development, QT/QTc interval prolongation was reported in the trelagliptin 800 mg group although it did not occur in the trelagliptin 200 mg group.

<For Alogliptin>

[Liver dysfunction or jaundice-related AEs]

Liver dysfunction or jaundice-related AEs are designated as AESIs because there are accumulated reports as serious adverse reaction.

10.1.5 Severity of adverse events

The severity of adverse events shall be classified and defined as shown below.

Mild	The event is transient and easily							
IVIIIQ	tolerated by the subject.							
Moderate	The event interrupts the subject's usual activities.							
Severe	The event causes considerable interference with the subject's usual activities.							

10.1.6 Causality of adverse events

The causal relationship of each adverse event to the study drug shall be classified and defined as shown below.

	An adverse event that follows an apparent temporal sequence (including clinical course
	after discontinuation). An adverse event the causal relationship could not be denied and
Related	there is reasonable possibility due to the study drug, although other factors such as
	underlying disease, concurrent diseases, or concomitant drugs/treatment are also
	suspected.
Not	An adverse event that does not follow an apparent temporal sequence from
related	administration of the study drug. Very likely due to other factors such as underlying

disease, concurrent diseases, or concomitant drugs/treatment.

10.1.7 Relationship to study procedures

The relationship shall be recorded as "Yes" if the principal investigator or investigator considers that there is reasonable possibility that an adverse event is due to a study procedure. Otherwise, the relationship shall be recorded as "No."

10.1.8 Date of onset

The date of onset of adverse events shall be determined according to the following rules:

Adverse event	Date of onset			
Signs, symptoms, diseases (diagnoses)	The date on which the first signs/symptoms were noted by the research subject and/or the principal investigator or investigator.			
Asymptomatic diseases	The date on which a diagnosis was confirmed through a test(s). The date on which a diagnosis was confirmed, even when the test results indicate an old sign(s) of the disease or an approximate time of its onset.			
Exacerbation of concurrent diseases	The date on which the first worsening of diseases/symptoms was noted by the research subject and/or the principal investigator or investigator.			
Onset of a test abnormality after the start of the study drug administration	The date on which a clinically significant laboratory abnormality was detected.			
Worsening of a baseline test abnormality after initiation of study treatment	The date on which a clear increase/decrease in a laboratory parameter was clinically confirmed based on the time profile of the parameter.			

10.1.9 Date of resolution

The date of resolution of an adverse event is the date on which the research subject recovered (including resolution with sequelae). If a research subject died due to the adverse event concerned, it shall be the date of death. The adverse event shall be recorded as "ongoing" if the research subject has not yet recovered by the end of the study.

10.1.10 Actions taken for the study drug

Actions taken for the study drug shall be classified or defined as shown below.

	Drug withdrawn	The study drug is discontinued because of an adverse event (including withdrawal by the research subject at his/her own discretion).
Drug withdrawn	When the treatment with the study drug is continued after withdrawal from the study, it shall be defined as "Dose not changed."	

	If the dose was unchanged after the onset of the adverse event it shall be defined as "Dose not changed."			
Dose not changed	If the study drug was discontinued, reduced, or increased because of another adverse event it shall be defined as "Dose not changed."			
	If the study drug was discontinued or reduced for a reason other than for the adverse event, e.g., inadvertence of the research subject, it shall be defined as "Dose not changed".			
Unknown	It has not been possible to determine what action has been taken because the research subject is lost to follow-up.			
Not Applicable	The study treatment had already been completed or discontinued before the onset of the adverse event.			
Dose reduced	The dose of the study drug was reduced because of the adverse event (including dose reduction by the research subject at his/her own discretion).			
Dose increased	The dose of the study drug was increased because of the adverse event (including dose increase by the research subject at his/her discretion).			
Washout	If the study treatment is suspended (i.e., interrupted) (including suspension/interruption by the research subject at his/her discretion) because of the adverse event but resumed thereafter, shall be defined as "washout".			

10.1.11 Outcome

Outcome of adverse events is classified as follows:

Category	Criteria				
Recovered	Disappearance or recovery of symptoms and findings Laboratory values returned to normal or baseline				
Improved	The intensity is lowered by one or more stages Symptoms or findings mostly disappeared Laboratory values improved, but have not returned to normal or baseline The research subject died from a cause other than the concerned adverse event while the condition was resolving (recording of the date of death unnecessary)				
Not recovered	No change in symptoms, findings, or laboratory data The symptoms, findings, or laboratory data on the final day of observable period were aggravated compared with the date of onset Irreversible congenital anomaly The research subject died from another cause before resolution of the concerned adverse event (recording of the date of death unnecessary)				
Recovered with sequelae	Disability that disturbs daily life				

Death	Direct relationship between death and the concerned adverse event "Direct relationship" means that the concerned adverse event was the cause of death, or the concerned adverse event was clearly responsible for death. Outcome of an adverse event which was not determined (judged, presumed) a direct cause of death observed in the same research subject is not considered as death. If outcome is death, the date of death shall be recorded.
Unknown	Follow-up specified in the protocol after the date of onset was not possible due to change of hospitals or relocation, etc.

10.2 Procedures

10.2.1 Collection and reporting of adverse events

10.2.1.1 Adverse event collection period

Collection of the adverse events shall commence at the start of administration of the study drug (Day 1) and shall continue until end of treatment (Day 29).

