7.2 Exclusion criteria

Research subjects meeting any of the criteria below shall not be included in this research.

- 1. Patients who received anti-diabetic medications within 4 weeks prior to the start of the observation period.
- Patients who have changed (including discontinuation or interruption) HMG-CoA reductase
 inhibitors or received new HMG-CoA reductase inhibitors ≤ 4 weeks before the start of the
 observation period.
- 3. Patients with clinically evident hepatic dysfunction (e.g., AST or ALT \geq 2.5-fold the upper limit of normal at the start of the observation period [Day -2])
- 4. Patients with moderate renal dysfunction, severe renal dysfunction or renal failure (e.g., creatinine clearance < 50 mL/min or serum creatinine > 1.4 mg/dL in men or > 1.2 mg/dL in women [equivalent to the creatinine clearance for persons aged 60 years with a body weight of 65 kg] at the start of the observation period [Day -2])
- 5. Patients with severe heart disease, cerebrovascular disorder, or severe pancreatic, hematologic or other diseases
- 6. Patients with a history of gastric or small intestinal resection
- 7. Patients with proliferative diabetic retinopathy
- 8. Patients warranting insulin therapy for glycemic control (e.g., patients with severe ketosis, diabetic coma or precoma, type 1 diabetes mellitus, severe infection, perioperative patients, or serious trauma)
- 9. Patients with a history of hypersensitivity or allergy to DPP-4 inhibitors
- 10. Patients who experience an allergic reaction to metal during CGM at the start of the observation period (Day -2)
- 11. Patients with any malignant tumors
- 12. Habitual drinkers whose average daily alcohol consumption is > 100 mL^{Note 1)}

- 13. Patients who have any contraindications for the study drug or are taking any contraindicated concomitant drugs listed in the package insert
- 14. Patients anticipated to require any prohibited concomitant medications during the study period
- 15. Patients who are day and night lifestyle reversal
- 16. Patients participating in any other clinical studies at the time of informed consent for this study
- 17. Pregnant women, nursing mothers, women who are possible pregnant, or women who plan to become pregnant
- 18. Other patients who are considered inappropriate for participation in this study in the opinion of the principal investigator or investigator

Note 1: Alcohol conversion table (for reference)

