7.5 Criteria for discontinuation or withdrawal of a research subject

The principal investigator or investigator shall record the main reason for discontinuation of protocol treatment on the case report form according to the classification described below. Refer section 9.1.12 for discontinuation case before randomization.

1. Adverse event

When the research subject had an adverse event that requires withdrawal of the research subject from the study because continued participation in the study would impose an unacceptable risk to the research subject's health, or when the research subject is unwilling to continue study participation because of the pretreatment event or adverse event.

2. Major protocol deviation

When it is discovered after randomization that a research subject does not meet the eligibility criteria or is not adhering to the protocol, and continued participation in the research would impose an unacceptable risk to the research subject's health.

3. Lost to follow-up

When the research subject failed to make visits and could not be contacted. The attempts that were made to contact the research subject shall be recorded in the source documents.

4. Voluntary termination

When the research subject wishes to withdraw from the research. The reason for discontinuation shall be recorded on the CRF when it is clarified.

5. Research termination

When the sponsor or a committee such as the IEC or regulatory authority has decided to terminate the study. Refer to Section 6.3.1 for details.

6. Pregnancy

When a female research subject is found to be pregnant.

Note: Research participation shall be immediately discontinued when pregnancy is known. Refer to Section 9.1.11 for procedure.

7. Others

Note: The specific reasons should be recorded on the CRF.

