9.1.6 Concurrent disease

A concurrent disease is defined as a disease or symptom that is present at the start of the observation period or that develops between the start of the observation period and the start of study treatment. Clinically significant abnormalities, including laboratory test data and physical examination findings, observed in tests and physical examinations at the start of study treatment shall be considered as a concurrent disease at the discretion of the principal investigator or investigator. The content of concurrent disease (diagnosis) shall be investigated.

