9.1.9 Continuous glucose monitoring (CGM)

Conducted according to Schedule of Research Procedures (Appendix A) Details shall be specified separately in the operation procedures manual.

- (1) Device used in this study
 - , leased from the sponsor.
- (2) Self-measurement of blood glucose (SMBG)

Use device leased from sponsor

Research subjects shall measure blood glucose levels every day during CGM in the observation and treatment periods. At least, blood glucose levels shall be measured at three time points on the first day of CGM ([1] at least 2 hours after the recorder is connected and [2] 2 hours after the first is measured. [3] at bedtime) and at four time points from the second day onward ([1] before breakfast, (2) before lunch, (3) before evening meal, and (4) at bedtime).

The glucose levels from SMBG shall be used for correction of glucose levels obtained from CGM.

(3) Observation period

A sensor shall be inserted at the start of the observation period (Day -2) and removed at the start of treatment (Day 1)

(4) Treatment period

A sensor shall be inserted (VISIT 3: Day 21), exchanged (VISIT 4: Days 24 to 26), and removed (VISIT 5: Day 29) during the treatment period.

(5) Dietetic therapy and exercise therapy

Research subjects shall present photographs of all meals to the principal investigator or investigator during CGM. Also, the meal provided by the sponsor shall be taken according to the calories prescribed by the sponsor for each research subject at the meal times shown below.

Time point of provision of meals: evening meal at start of observation period (Day-2), evening meal on first and seventh of CGM to be performed from Day 21 for 9 days.

Research subjects shall only conduct exercise therapy feasible (if performed) under the same conditions every day during CGM.

The principal investigator or investigator shall prescribe consistent dietetic therapy and exercise therapy (if performed) throughout the research period. Compliance with dietetic therapy and exercise therapy(if performed) shall be investigated and rated on a four-point scale as follows:

- 1. Compliant (compliance rate $\geq 90\%$)
- 2. Almost compliant (compliance rate $\geq 70\%$)
- 3. Generally compliant (compliance rate $\geq 50\%$)
- 4. Minimally compliant (compliance rate < 50%)

(6) Research subject diary

Research subjects shall complete the subject diary every day during CGM and submit the diary to the principal investigator or investigator.

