10.1.2 Considerations for adverse events

Generally unfavorable findings are described below:

- Newly diagnosed disease or unexpected aggravation of existing symptom (intermittent event of an existing symptom is not considered an adverse event)
- Requiring action or medical practice
- Requiring invasive diagnostic treatment
- Requiring discontinuation or a change in the dose of the study drug or a concomitant medication
- Considered unfavorable by the principal investigator or the investigator

Diagnosis name and signs/symptoms:

Adverse events shall be recorded by diagnosis name. Accompanying signs (including abnormal laboratory values, abnormal ECG findings) and symptoms shall not be recorded as adverse events. If an adverse event could not be expressed by a diagnosis name, the signs or symptoms shall be recorded as the adverse event.

Laboratory test values and ECG findings:

Abnormal laboratory values and ECG findings shall be recorded as adverse events when the principal investigator or investigator judges the results are clinically problematic (in other words, when certain action or medical practice is required, or when the principal investigator or the investigator judges the change has exceeded the normal physiological variation range of the research subject). Retest and/or continued monitoring of an abnormality are not considered medical practice.

Also, repeated or additional conduction of non-invasive tests for verification, evaluation, and monitoring of an abnormality are not considered medical practice.

However, when abnormal laboratory values and ECG findings are the accompanying symptoms of a disease diagnosed as an adverse event (e.g., increased creatinine due to renal dysfunction, etc.), the adverse event shall be handled by its diagnosis name.

Pre-existing conditions (disease or symptom that has been present since before the start of study treatment): Pre-existing disease or symptom that has been present since before the start of study treatment shall be regarded as a concurrent disease and not an adverse event. When a concurrent medical condition is aggravated, the aggravation shall be determined as an adverse event and the principal investigator or the investigator shall record on the CRF that the adverse event is an aggravation of the concurrent disease (e.g., "aggravation of hypertension," etc.).

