10.2.2 Collection and reporting of serious adverse events

When a serious adverse event develops during the period of collecting adverse events, it shall be reported according to the following procedures. At the time of onset of a serious adverse event or notification of the onset by the research subject, the principal investigator shall report the serious adverse event to the chief executive of the research implementing entity immediately, and the sponsor or CRO to whom the sponsor has entrusted responsibility shall notify the principal investigator of the research implementing entity.

The principal investigator shall then report the serious adverse event to the sponsor (for the contact information, refer to the attachment) within 1 day of notification of the event onset. Further, the principal investigator shall submit a formal report within 10 calendar days to the sponsor.

Furthermore, it shall be mandatory to include the contents below in the report to be submitted to the sponsor within 1 working day, and other items shall be reported as far as possible.

- Brief description of adverse event and the reason for why it was determined as serious
- Research subject ID number
- Name of principal investigator or the investigator
- Name of the study drug
- Determined causal relationship

The principal investigator or investigator shall report spontaneously reported serious adverse events that are collected even after the adverse event collection period to the sponsor.

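### Adverse event collection opens at the first dose, 2 to 4 days after the first study-only invasive procedures, so a pre-dose procedure-related event is filed as concurrent disease and has no written SAE route

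*Protocol*

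**What the plan says.** All references are to the current protocol version and the SAP.

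- **Collection period.** Under 10.2.1.1, "Collection of the adverse events shall commence at the start of administration of the study drug" on Day 1, and it runs to Day 29. Section 9.3.1 (Visit 1) has no adverse event item; the item first appears in 9.3.2 (Visit 2, Day 1).
- **First procedures.** Section 9.1.9 (3) puts a sensor in at Day -2 and takes it out at the start of treatment. Laboratory sampling is also at Visit 1 (9.3.1, Appendix A). Appendix A allows Visit 1 on Day -4 to Day -2, and the SAP time windows repeat that range.
- **Classification.** Section 9.1.6 counts as concurrent disease anything that "develops between the start of the observation period and the start of study treatment", and asks for its diagnosis. Section 10.1.2 says that a condition present before treatment "shall be regarded as a concurrent disease and not an adverse event".
- **Serious events.** Section 10.1.3 defines an SAE as an event arising after a pharmaceutical product has been given. Section 10.2.2 reads: "When a serious adverse event develops during the period of collecting adverse events, it shall be reported according to the following procedures". Its only extension is to spontaneous reports received after the period.
- **Harm foreseen.** Exclusion criterion 10 names "Patients who experience an allergic reaction to metal during CGM" at the start of the observation period. Section 7.5 mentions a subject "unwilling to continue study participation because of the pretreatment event or adverse event", but no section defines, collects or reports a pretreatment event.

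**The concern.** Starting collection at the first dose is a common choice when the only question is drug safety. Here, subjects undergo invasive procedures for the study alone before any drug is given, and the protocol expects at least one kind of harm from them. It also asks for each adverse event's relationship to study procedures (10.1.7), yet the collection period leaves out the first such procedures.

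The text goes beyond silence, because it assigns these events to a background-disease category. What is at stake is oversight. A sensor-site reaction or a procedure-related hospitalization before dosing would lack the data items by which the sponsor and the ethics committee could recognize it as harm caused by the study. If it were serious, nothing in the protocol would require anyone to be told.

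**Working it through.** **1. The plan's own figure.** Appendix A calls the day before Day 1 Day -1, so there is no Day 0. Days -2 and -1 plus Days 1 to 29 give 2 + 29 = 31 days, the stated duration of evaluation.

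**2. The uncovered interval.** Counting back from Day 1 with no Day 0:

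- Visit 1 on Day -2: 2 days to the first dose.
- Visit 1 on Day -4: 4 days to the first dose.

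Collection therefore covers 29 of 31 nominal days, or 29 of 4 + 29 = 33 at the Day -4 limit. Sensor removal on Day 1 is probably outside too, since 8.1.2 gives the drug after the required tests and observations.

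**3. The same event on either side of the first dose.**

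| | Onset after first dose | Onset from Visit 1 to first dose |
|---|---|---|
| Class | Adverse event (10.1.1) | Concurrent disease (9.1.6, 10.1.2) |
| Required record | Term, dates, severity, drug and procedure causality, action, outcome, seriousness (10.2.1.2) | Diagnosis (9.1.6) |
| If serious | To the head of the institution and the sponsor (10.2.2), then the ethics committee (10.3.1) | Outside the 10.2.2 trigger; a pre-dose event also does not fit 10.1.3 |
| Reason for leaving | Adverse event category (7.5) | If before randomization, a list with no such category (9.1.12) |
| SAP output | Treatment-emergent tables (8.1) | Concurrent disease in dosed subjects (6.2.2); if not randomized, the reason for that (6.1.2) |

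The steps in 10.3.1 start from the investigator's report, so they do not begin if 10.2.2 does not apply.

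**4. Cases that are covered.** A reaction to the first sensor that begins after dosing is an adverse event. So is a pre-dose condition that worsens after dosing (10.1.2). On the nominal schedule, the Visit 3 insertion and the Visit 4 exchange fall inside the period.

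**5. Exposure.**

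- By wear time: 2 baseline days + 9 treatment days = 11 nominal CGM days, of which 2 are uncovered (2/11 = 18%).
- By insertions: Visits 1, 3 and 4 make 3 per subject. At the planned minimum of 30 evaluable subjects, 30 × 3 = 90 insertions, of which 30 × 1 = 30 precede collection.

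Neither is an event count. The documents give no rate of sensor reactions or of SAEs.

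**6. Where collection would need to start.** Consent may be as early as Day -28, but Appendix A shows no sensor and no blood test before Visit 1. Starting at Visit 1 closes the gap.

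**The case against.** The strongest reply is that such events would not vanish. Section 7.4 (12) has subjects report symptoms with onset, degree and outcome at visits. Section 10.2.1.2 requires a symptom check at each visit, and at Visit 2 its sample question reaches back to Visit 1. Section 9.1.12 allows free text under voluntary discontinuation and other reasons, and SAP 6.1.2 tabulates reasons for non-randomization in all consented subjects. This stands: some trace would usually remain. It does not close the gap, because a symptom reported at Visit 2 with pre-dose onset is still not an adverse event under 10.1.2, and none of these texts asks for seriousness or procedure causality. Appendix B items 10 and 12 and section 15.10 do not help either. They deal with medical care, with reporting that is already required, and with compensation.

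A reader might infer more than the documents support:

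- **That sensor-related event rates will be biased low.** No such rate is planned. Protocol 13.1.6 and SAP 8.1 tabulate by drug relationship, severity, seriousness, death and discontinuation, not by relationship to procedure. Reactors are removed by exclusion criterion 10, not by the collection window.
- **That a third of sensor risk is missed.** The 30 of 90 counts insertions; by nominal wear time the share is 2 of 11.
- **That 10.3.1 was meant to catch procedure-related events because it refers to causality with the study.** A parenthesis there equates the study with the study drug, so the phrase cannot carry that weight.

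**Conclusion.** The gap is real and follows from the wording of several sections read together. For 2 days nominally, and at most 4, subjects are exposed to study-only invasive procedures. An event with onset in that time is classed as background disease, without severity, seriousness or relationship to procedure, and a serious one has no written route.

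The effect is on safety oversight, not on the treatment comparison: the drug-related treatment-emergent comparisons and every planned table are unaffected. The number of events concerned is unknown. That it is small is a judgement from the short interval and the planned minimum of 30 evaluable subjects, not a figure in the documents. The conclusion assumes that the protocol is followed as written and that no separate manual or CRF instruction, unavailable here, supplies the missing items. The correction is cheap and should be made, but the point does not threaten the trial's results.

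**What to change.** Amend the protocol as follows.

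- **10.2.1.1 and 10.2.2:** start AE and SAE collection, and SAE reporting, at the first study-specific procedure (Visit 1). Starting at consent is not needed for this purpose.
- **9.1.6 and 10.1.2:** take events that begin between Visit 1 and the first dose out of concurrent disease. Record them as pretreatment events with severity, seriousness and relationship to study procedure.
- **10.1.1 and 10.1.3:** extend the definitions to this category. Otherwise a pre-dose hospitalization would still fail the SAE definition, which depends on a product having been given.
- **9.1.12:** add the same items to the page for subjects withdrawn before randomization.
- **Appendix A:** align the adverse event row.

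In the SAP, keep the section 8 treatment-emergent tables to onset after the first dose. Add one listing of pretreatment events for all consented subjects, since the only listing in section 9 is limited to randomized subjects.

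The cost is one amendment, a few CRF fields, some additional minor pre-dose records and one listing. No visit, test or efficacy analysis changes.
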